### **5.6.3 Additional safety assessments**

Assessments in relation to planned safety laboratory measurement, body measurements, vital signs and physical examinations are defined in section [6.2](#). The assessments will be presented using descriptive statistics as described in section [5.1](#). Number of patients with a positive antibody test will be presented as described in section [5.1](#) and furthermore a list of all positive antibodies recorded during the trial will be presented.

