| Number of injection site reactions               | 
Concizumab
 

Before the pausec: From start of treatment (week 0b) up until 7 weeks after the treatment was paused

 
as well as
 

After the pausec: From start of concizumab treatment up until the end of trial (week 167)

                                                                                                                                                                                                                                                                                                                                                                                                                                                         |       |
| Number of patients with antibodies to concizumab | 
Concizumab (arms 2-4)
 

Before the pausec: From start of concizumab treatment (week 0b) up until 7 weeks after the treatment was paused

 
as well as
 

After the pausec: From start of concizumab treatment (week 0a) up until the primary analysis cut-off (at least 32 weeks)

 
Concizumab (arm 1 extension part)
 

From start of the new concizumab dosing regimen (visit 9a) up until the primary analysis cut-off

                                                                                                                                                                                        | Count |

| Endpoint title                                                     | Time frame                                                                                                                                                                                                                                                                                                                                                              | Unit     |

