### Treatment arm 3:

The HAwI and HBwI patients enrolled into the concizumab phase 2 trial (NN7415-4310 (explorer 4)) at time of transfer will be offered enrolment into arm 3 (approximately 25 patients). It

is required that these patients are on concizumab prophylaxis up until enrolment into the trial. These patients will continue concizumab PPX and have a combined visit 1 and 2. All patients from 4310 were transferred to trial 4311 before the pause. Upon restart, patients will receive the new concizumab dosing regimen.

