### 9.4.7 Immunogenicity assessments

Samples for the determination of anti-drug antibodies will be collected according to the flowchart in Section [2](#). All patients will have samples drawn at V1/V1a, but only patients randomised/allocated to concizumab treatment (arms 2, 3 and 4) will have samples drawn at the remaining indicated timepoints in the main part of the trial. In the extension part of the trial, samples must be drawn for all patients (arms 1–4). Sampling should always take place prior to administration of concizumab. In case of suspected hypersensitivity reaction requiring systemic treatment, additional blood samples are to be collected; refer to Section [9.4.8](#).

Assessment of binding antibodies against concizumab (anti-drug antibodies (ADA) will be performed at specialised laboratories whereas assessment of neutralising antibodies will be performed at Novo Nordisk.

Analysis for ADA will be done with a bridging ECL assay (binding ADA assay) using labelled concizumab for antibody capture and detection. If a sample is confirmed positive in the confirmatory assay, the sample is considered positive for binding antibodies. Confirmed positive samples will be characterised in a specificity assay for binding to IgG backbone or the S241P mutation. Furthermore, positive samples will be characterised for neutralising activity using a neutralising ADA assay. All antibody assays are validated according to international guidelines and recommendations.

The following data will be available:

- Anti-concizumab antibodies
- Anti-concizumab antibody titres
- Anti-concizumab binding antibodies cross-reacting with IgG4 backbone or S241P mutation

- Anti-concizumab neutralising antibodies

The samples will be analysed and reported to sites at the primary analysis cut-off and at end of extension part (end of trial). A detailed description of the assay methods will be included in the antibody analysis report at the end of the trial.

Patients positive for binding antibodies at end of follow-up may be followed outside this protocol.

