	
For subjects in arms 2-4 that are only exposed to the initial concizumab dosing regimen, the period begins at the time of start of the initial concizumab PPX regimen.
 
For subjects in arms 2-4 that start on the new concizumab dosing regimen and who have been exposed to the initial dosing regimen, the period consists of two periods with a pause in between. The first period begins at the time of start of the initial concizumab PPX regimen and ends 7 weeks after the treatment was paused while the second period begins at the time of start of the new concizumab PPX regimen.
 
For all cases of arms 2-4 above the periods end at the first occurrence of:
 

• Items 2., 3., 4., 5. or 6. above

On-treatment without data on initial regimen	
The time period where subjects are considered to be affected by on-demand treatment or treatment with the new concizumab dosing regimen.
 
The analysis data set is defined similarly as the ‘on-treatment’ analysis data set with the exception:
 

• Observation time during the initial concizumab PPX regimen is excluded

On-treatment without ancillary therapy a excl. data on initial regimen for subjects exposed to both regimens	
The time period where subjects are treated by either the new concizumab dosing regimen or the initial concizumab dosing regimen (only included if not exposed to the new concizumab dosing regimen) or are treated by on-demand treatment and additionally have not used factor-containing products not related to treatment of a bleed during any of the cases.
 
The analysis data set is defined similarly as the ‘on-treatment’ analysis data set with the exception:
 

• Periods where factor containing products not related to treatment of a bleed have been used are excluded

• For subjects in arms 2-4 that start on the new concizumab dosing regimen and who have been exposed to the initial dosing regimen, the data on the initial concizumab PPX regimen are excluded

a Ancillary therapy is defined as use of factor-containing products not related to treatment of a bleed.

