**Table 1 Analysis sets used for analyses and/or presentations of endpoints/assessments**

Endpoint/assessment categories a	Subject Analysis Set	Analysis Data Sets
Bleeding episodes	FAS	On-treatment without ancillary therapy excl. data on initial regimen for subjects exposed to both regimens
PK, PD and safety not relating to events	SAS	On-treatment without data on initial regimen
Safety relating to events b	SAS	On-treatment and On-treatment without data on initial regimen

aWhich endpoints/assessments that belong under each category can be found in section 9 of the protocol version 7.

bThis specifically refers to: number of thromboembolic events, number of hypersensitivity type reactions, number of injection site reactions, number of patients with antibodies to concizumab, and number of adverse events.

For arms 2-4 the target joints registered at baseline will be used for the assessment done at week 56. For arm 1 the target joint evaluation done at visit V9a will be used for assessment at week 56.

Continuous endpoints/assessments will be presented using descriptive statistics which will include min, max, mean, SD, median, and quartiles. For PK endpoints/assessments, the descriptive statistics will also include geometric mean and geometric CV. Event data (including AEs) will be summarised including number of subjects with an event/episode, percentage of subjects with an event/episode, number of events/episodes and rate of events/episodes. Categorical assessments will be summarised by number and percent of subjects in each category. Presentations of results will be by arm and visit (when applicable) and when relevant arm 1 will be split into two parts with on-demand treatment and concizumab treatment.

Baseline for the assessments done at week 56 is defined as the latest non-missing measurement recorded before the time of the first administration of concizumab with the new dosing regimen (arms 2-4 and arm 1 after receiving concizumab) or recorded before randomisation to the on-demand administration (arm 1). If this measurement is missing for arms 2-4 or a subject from arms 2-4 chooses not to restart on concizumab, then the baseline obtained prior to the initial dosing regimen will be used (if available). If the V9a measurement is missing for arm 1 concizumab part,

the latest measurement recorded prior to V9a will be used as a concizumab baseline for arm 1 subjects.

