Assessment	Endogenous thrombin potential (ETP)	At visits where thrombin generation assessments are planned to be measured in the trial up to 56 weeks	nmol/L*min		5.5.2
Assessment	Endogenous thrombin Potential ratio	At visits where thrombin generation assessments are planned to be measured in the trial up to 56 weeks	Ratio		5.5.2
Assessment	Velocity index	At visits where thrombin generation assessments are planned to be measured in the trial up to 56 weeks	nmol/L*min		5.5.2
Assessment	Thrombin lag time	At visits where thrombin generation assessments are planned to be measured in the trial up to 56 weeks	min		5.5.2

Assessment	Time to thrombin peak	At visits where thrombin generation assessments are planned to be measured in the trial up to 56 weeks	min		5.5.2
Assessment	Number of adverse events	On demand (arm 1) • From randomisation to on demand treatment up until start of concizumab treatment	Count	Week 56 cut-off is when all patients from arm 2-4 have completed visit 13a assessments or permanently discontinued treatment.	5.6.2
Assessment	Number of thromboembolic events	Concizumab (arm 1) • From start of the new concizumab dosing regimen up until week 56 cut-off	Count	Concizumab (arm 1) data available up until week 56 cut-off will be presented.	5.6.2
Assessment	Number of hypersensitivity type reactions	Concizumab (arms 2-4) • Before the pause: From start of concizumab treatment (week 0) up until 7 weeks after the treatment pause  as well as  • After the pause: From start of the new concizumab treatment (week 0) up until week 56 cut-off	Count		5.6.2
Assessment	Number of injection site reactions				5.6.2

Assessment	Number of patients with antibodies to concizumab	Concizumab (arms 2-4) 
 
From start of the new concizumab dosing regimen (week 0) up until week 56 cut-off
 
	Count	
Week 56 cut-off is when all patients from arm 2-4 have completed visit 13a assessments or permanently discontinued treatment.
	5.6.3

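### The week-56 antibody count ignores antibody status before the first new-regimen dose, so antibodies persisting from earlier concizumab exposure are counted alongside new ones

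*SAP*

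**What the plan says.** The protocol endpoint (4.3.2.2) is "Number of patients with antibodies to concizumab", a plain patient count. The week-56 SAP carries it over. Section 5.6.3 states that "Number of patients with a positive antibody test will be presented as described in section" 5.1, and adds that "a list of all positive antibodies recorded during the trial will be presented".

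In SAP Table 1 the endpoint is grouped with event data: footnote b names "number of injection site reactions, number of patients with antibodies to concizumab, and number of adverse events". These are summarised on the safety analysis set using two data sets, one covering all on-treatment time and one leaving out the initial regimen. Appendix 2 gives the antibody window for arms 2-4 as "From start of the new concizumab dosing regimen (week 0) up until week 56 cut-off". For the data set without the initial regimen, the stated difference (SAP section 4) is that "Observation time during the initial concizumab PPX regimen is excluded".

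On sampling, protocol 9.4.7 says "All patients will have samples drawn at V1/V1a", requires sampling before dosing, and lists titres among the available data. The section 2 flowchart adds an antibody sample at visit 2a for arms 2-4. On earlier exposure, the protocol's description of arm 3 says it is "required that these patients are on concizumab prophylaxis up until enrolment into the trial", and that all phase 2 patients had transferred before the pause.

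**The concern.** A reader of the week-56 report will want to know how often antibodies appear on the new dosing regimen. The count answers a different question: how many patients have a positive sample while on it. The two agree only if nobody was positive at the start. Here many patients were not concizumab-naive at that point. Arm 3 had been treated in phase 2 and again in this trial before the pause, and restarters in arms 2 and 4 had received the initial regimen.

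An antibody that persists across the pause therefore enters the new-regimen figure. Arm 3 and restarters could then look more immunogenic than first-exposed patients for reasons unrelated to the new regimen. This matters because protocol 3.3 links vascular changes in animal studies to immune complexes of concizumab and antibodies against it, and reports a severe hypersensitivity reaction in phase 3 before the pause.

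**Working it through.** **Planned numbers (protocol Table 2).**
- Arm 1: 9 + 8 = 17. Arm 2: 18 + 16 = 34. Arm 3: up to 15 + 10 = 25. Arm 4: 60.
- Total: 17 + 34 + 25 + 60 = 136, which reproduces the protocol's stated enrolment.
- Arms 2-4: 34 + 25 + 60 = 119. Arm 3 share: 25/119 = 21.0%.

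**Does any rule use earlier status?**
- SAP 5.6.3: a positive test is the only condition.
- SAP 5.1: a general baseline is defined (last measurement before the first new-regimen dose), but no text applies it to antibodies.
- SAP section 4: the data set without the initial regimen drops observation time. It does not drop patients who were already positive.
- SAP Appendix 2: a time window only.

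So a patient positive at visit 2a and again at any later on-treatment sample is counted on the new regimen.

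**Weight of one such patient.** In arms 2-4: 1/119 = 0.84 percentage points. In arm 3: 1/25 = 4 points.

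**Illustration, on assumed rates.** The documents give no antibody rates. Suppose 10% of baseline-negative patients become positive, and 5-30% of pre-exposed patients are positive at baseline and stay positive. With c carried-over patients among n:

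crude rate = [c + 0.10 × (n − c)] / n

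| Pre-exposed group (assumed) | c | Crude rate |
|---|---|---|
| Arm 3 only (25), n = 119 | 1.25 to 7.5 | 10.9% to 15.7% |
| Arm 3 plus 40 restarters (65), n = 119 | 3.25 to 19.5 | 12.5% to 24.7% |
| Within arm 3, n = 25 | 1.25 to 7.5 | 14.5% to 37.0% |

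Example: (7.5 + 0.10 × 111.5)/119 = 18.65/119 = 15.7%. In every row the rate among baseline-negative patients is 10.0% by construction. The 40 restarters are an assumption, since the documents give no number. With no carry-over (c = 0) the crude rate is also 10.0%.

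**The case against.** Several points on the other side stand.

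- The endpoint is worded as presence of antibodies, not onset, and the documents do not call it incidence. That is a reason to keep the count. It does not supply the new-onset figure.
- The listing of all positives lets a reader trace persistent positivity patient by patient in a trial of this size. It does not change the tabulated count.
- Results are shown by arm, so arm 3 is already separate. Restarters and new patients within arms 2 and 4 are not.
- SAP section 1 leaves derivation details to the analysis data reviewer's guide, and the main-part analyses to the SAP for the primary analysis cut-off. Neither is available here, so a rule in one of them cannot be excluded.
- The week-56 outputs are descriptive and test no hypothesis.

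Three stronger readings are tempting and are not supported.

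- A reader might infer that a patient positive both before and after the pause is counted twice. In SAP section 4 the on-treatment data set is one set made of two periods, the data set without the initial regimen is an overlapping second presentation, and the endpoint counts patients. Nothing adds counts from two windows.
- A reader might infer that every positive sample counts. Samples are taken before dosing and the window opens at the start of treatment, so a patient positive only at visit 1a or 2a is not counted on the new regimen. Carry-over needs a later positive sample.
- A reader might infer that non-specific assay reactivity enters unchecked. Protocol 9.4.7 requires a confirmatory assay, and then characterises specificity and neutralising activity.

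**Conclusion.** The point holds for the week-56 antibody summary as written: patients already positive before the first new-regimen dose, and positive again afterwards, are not distinguished from new positives. All of arm 3 (up to 25 of 119 planned) and an unstated number of restarters in arms 2 and 4 could be affected. The size is unknown and may be zero. It is bounded only by the number of pre-exposed patients who remain positive, at 0.84 points each in arms 2-4 or 4 points each in arm 3. These figures use planned enrolment; actual denominators will differ.

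This is a modest improvement to a descriptive safety table. It rests on the supplied SAP text and lapses if the reviewer's guide already defines treatment-emergent antibodies for this output.

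**What to change.** Keep the protocol-defined count. Add rows to the antibody table, by arm and by prior exposure (phase 2, initial regimen, none):

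1. Patients positive in the last sample before the first dose of the period analysed, split by titre raised or not raised afterwards. The SAP should state what rise counts.
2. Patients negative in that sample and positive afterwards (treatment-emergent).
3. Patients without a baseline sample.

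For the on-treatment data set, take the last sample before first exposure in this trial. For the data set without the initial regimen, take the last sample before the first new-regimen dose. Arm 3 is pre-exposed on either definition, which is why the prior-exposure split is needed.

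Label each row with its data set, because Table 1 assigns both sets to this endpoint while Appendix 2 gives only the new-regimen window for arms 2-4.

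The cost is one derivation and a few table rows, with no new sampling. The drawback is small numbers per row, so counts should be shown beside percentages.

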## **5.7 Subgroup analyses**

Descriptive statistics by subgroups are specified for haemophilia types (HAWI or HBWI) above in each of the sections concerning the specific assessments, such as bleed related endpoints.

## **5.8 Interim analyses**

No formal interim analyses are planned.

Several evaluations are to be made during the conduct of the trial:

- at the primary analysis cut-off
- after 56 weeks
- at the end of the extension part

After the initial evaluation at the primary analysis cut-off no further confirmatory conclusions can be made.

### **5.8.1 Data monitoring committee**

A Data Monitoring Committee (DMC) is established to review and evaluate accumulating data from the trial in order to protect the safety of the subjects.

The DMC members are not having direct contact with any Novo Nordisk staff involved with the trial except for Novo Nordisk global safety. Details in relation to DMC can be seen in Appendix 4 of the protocol version 7.

## 6 Supporting documentation

### 6.1 Appendix 1: List of abbreviations

ABR	Annual Bleeding Rate
ADRG	Analysis Data Reviewer's Guide
AE	Adverse event
AESI	Adverse event of special interest
AUC	Area under the curve
DMC	Data monitoring committee
FAS	Full analysis set
HAwI	Haemophilia A with inhibitors
HBwI	Haemophilia B with inhibitors
IWRS	interactive web response system
LLoQ	Lower limit of quantification
MedDRA	Medical dictionary for regulatory activities
PACO	Primary analysis cut-off
PD	Pharmacodynamic
PK	Pharmacokinetic
PPX	Prophylaxis
SAP	Statistical Analysis Plan
SAS	Safety analysis set
TFL	tables, figures and listings
TFPI	Tissue factor pathway inhibitor

## 6.2 Appendix 2: Definition of exploratory efficacy/safety endpoints and assessments

Type	Title	Time frame	Unit	Details	Section
Assessment	Number of treated spontaneous and traumatic bleeding episodes	On demand (arm 1) 
 
From randomisation (week 0) up until start of concizumab treatment (at least 24 weeks)
 
 Concizumab (arm 1) 
 
From start of the new concizumab dosing regimen up until week 56 cut-off
 
 Concizumab (arms 2-4) 
 
From start of the new concizumab dosing regimen (week 0) up until week 56 cut-off
 
	Count	
Week 56 cut-off is when all patients from arm 2-4 have completed visit 13a assessments or permanently discontinued treatment.
 
Concizumab (arm 1) data available up until week 56 cut-off will be presented.
	5.5.1
Assessment	Number of treated spontaneous bleeding episodes	On demand (arm 1) 
 
From randomisation (week 0) up until start of concizumab treatment (at least 24 weeks)
 
 Concizumab (arm 1) 
 
From start of the new concizumab dosing regimen up until week 56 cut-off
 
	Count	
Week 56 cut-off is when all patients from arm 2-4 have completed visit 13a assessments or permanently discontinued treatment.
 
Concizumab (arm 1) data available up until week 56 cut-off will be presented.
	5.5.1

		Concizumab (arms 2-4) 
 
From start of the new concizumab dosing regimen (week 0) up until week 56 cut-off
 
			
Assessment	Number of treated spontaneous and traumatic joint bleeds	
On demand (arm 1)
 
 
From randomisation (week 0) up until start of concizumab treatment (at least 24 weeks)
 
 
Concizumab (arm 1)
 
 
From start of the new concizumab dosing regimen up until week 56 cut-off
 
 
Concizumab (arms 2-4)
 
 
From start of the new concizumab dosing regimen (week 0) up until week 56 cut-off
 
	Count	
Week 56 cut-off is when all patients from arm 2-4 have completed visit 13a assessments or permanently discontinued treatment.
 
Concizumab (arm 1) data available up until week 56 cut-off will be presented.
	5.5.1
Assessment	Number of treated spontaneous and traumatic target joint bleeds	
On demand (arm 1)
 
 
From randomisation (week 0) up until start of concizumab treatment (at least 24 weeks)
 
 
Concizumab (arm 1)
	Count	
Week 56 cut-off is when all patients from arm 2-4 have completed visit 13a assessments or permanently discontinued treatment.
 
Concizumab (arm 1) data available up until week 56 cut-off will be presented.
	5.5.1

		
 
From start of the new concizumab dosing regimen up until week 56 cut-off
 
 
Concizumab (arms 2-4)
 
 
From start of the new concizumab dosing regimen (week 0) up until week 56 cut-off
 
			
Assessment	The number of all spontaneous and traumatic bleeds (treated and untreated)	
On demand (arm 1)
 
 
From randomisation (week 0) up until start of concizumab treatment (at least 24 weeks)
 
 
Concizumab (arm 1)
 
 
From start of the new concizumab dosing regimen up until week 56 cut-off
 
 
Concizumab (arms 2-4)
 
 
From start of the new concizumab dosing regimen (week 0) up until week 56 cut-off
 
	Count	
Week 56 cut-off is when all patients from arm 2-4 have completed visit 13a assessments or permanently discontinued treatment.
 
Concizumab (arm 1) data available up until week 56 cut-off will be presented.
	5.5.1
Assessment	Pre-dose concizumab plasma concentration	
Concizumab (arms 2-4)
 
 
From start of the new concizumab dosing
 
	ng/mL	Summary of pre-dose assessments from start of the new concizumab dosing regimen (week 0) up until week 56.	5.5.2

		regimen (week 0) up until week 56 cut-off			
Assessment	Thrombin peak	At visits where thrombin generation assessments are planned to be measured in the trial up to 56 weeks	nmol/L	Summary of these assessments up until week 56.  From start of the new concizumab dosing regimen (week 0) up until week 56.	5.5.2
Assessment	Free TFPI concentration	At visits where free TFPI assessments are planned to be measured in the trial up to 56 weeks	ng/mL		5.5.2
Assessment	Endogenous thrombin potential (ETP)	At visits where thrombin generation assessments are planned to be measured in the trial up to 56 weeks	nmol/L*min		5.5.2
Assessment	Endogenous thrombin Potential ratio	At visits where thrombin generation assessments are planned to be measured in the trial up to 56 weeks	Ratio		5.5.2
Assessment	Velocity index	At visits where thrombin generation assessments are planned to be measured in the trial up to 56 weeks	nmol/L*min		5.5.2
Assessment	Thrombin lag time	At visits where thrombin generation assessments are planned to be measured in the trial up to 56 weeks	min		5.5.2

Assessment	Time to thrombin peak	At visits where thrombin generation assessments are planned to be measured in the trial up to 56 weeks	min		5.5.2
Assessment	Number of adverse events	On demand (arm 1) • From randomisation to on demand treatment up until start of concizumab treatment	Count	Week 56 cut-off is when all patients from arm 2-4 have completed visit 13a assessments or permanently discontinued treatment.	5.6.2
Assessment	Number of thromboembolic events	Concizumab (arm 1) • From start of the new concizumab dosing regimen up until week 56 cut-off	Count	Concizumab (arm 1) data available up until week 56 cut-off will be presented.	5.6.2
Assessment	Number of hypersensitivity type reactions	Concizumab (arms 2-4) • Before the pause: From start of concizumab treatment (week 0) up until 7 weeks after the treatment pause  as well as  • After the pause: From start of the new concizumab treatment (week 0) up until week 56 cut-off	Count		5.6.2
Assessment	Number of injection site reactions				5.6.2

Assessment	Number of patients with antibodies to concizumab	Concizumab (arms 2-4) 
 
From start of the new concizumab dosing regimen (week 0) up until week 56 cut-off
 
	Count	
Week 56 cut-off is when all patients from arm 2-4 have completed visit 13a assessments or permanently discontinued treatment.
	5.6.3
Assessment	Change in <safety laboratory parameter>	On demand (arm 1) 
 
From randomisation (week 0) up until start of concizumab treatment (at least 24 weeks)
 
 Concizumab (arm 1) 
 
From start of the new concizumab dosing regimen up until week 56 cut-off
 
 Concizumab (arms 2-4) 
 
From start of the new concizumab dosing regimen (week 0) up until week 56 cut-off
 
 From start of treatment (week 0) to every visit where the <safety laboratory parameter> is planned to be measured up until V13a (week 56)	Multiple units	
<safety laboratory parameter> refers to each safety laboratory parameter for haematology, biochemistry and coagulation parameters as listed in table 18 of the protocol version 7.
 
Week 56 cut-off is when all patients from arm 2-4 have completed visit 13a assessments or permanently discontinued treatment.
 
Concizumab (arm 1) data available up until week 56 cut-off will be presented.
	5.6.3

Assessment	Change in body weight	On demand (arm 1)	kg	Week 56 cut-off is when all patients from arm 2-4 have completed visit 13a assessments or permanently discontinued treatment.	5.6.3
		• From randomisation (week 0) up until start of concizumab treatment (at least 24 weeks)		Concizumab (arm 1) data available up until week 56 cut-off will be presented.	
		Concizumab (arm 1)			
		• From start of the new concizumab dosing regimen up until week 56 cut-off			
Assessment	Change in systolic blood pressure	Concizumab (arms 2-4)	mmHg	Week 56 cut-off is when all patients from arm 2-4 have completed visit 13a assessments or permanently discontinued treatment.	5.6.3
		• From start of the new concizumab dosing regimen (week 0) up until week 56 cut-off		Concizumab (arm 1) data available up until week 56 cut-off will be presented.	
		From start of treatment (week 0) to every visit where body weight is planned to be measured up until V13a (week 56)			
Assessment	Change in diastolic blood pressure	On demand (arm 1)	mmHg	Week 56 cut-off is when all patients from arm 2-4 have completed visit 13a assessments or permanently discontinued treatment.	5.6.3
		• From randomisation (week 0) up until start of concizumab treatment (at least 24 weeks)		Concizumab (arm 1) data available up until week 56 cut-off will be presented.	
		Concizumab (arm 1)			
Assessment	Change in pulse rate	Concizumab (arm 1)	beats/min	Concizumab (arm 1) data available up until week 56 cut-off will be presented.	5.6.3

		
 
From start of the new concizumab dosing regimen up until week 56 cut-off
 
 
Concizumab (arms 2-4)
 
 
From start of the new concizumab dosing regimen (week 0) up until week 56 cut-off
 
 
From start of treatment (week 0) to every visit where the vital signs are planned to be measured up until V13a (week 56)
			
Assessment	Change in physical examination	
Concizumab (arm 1)
 
 
From start of the new concizumab dosing regimen up until week 56 cut-off
 
 
Concizumab (arms 2-4)
 
 
From start of the new concizumab dosing regimen (week 0) up until week 56 cut-off
 
 
From start of treatment (week 0) to every visit where physical examination is planned to
	%	
Week 56 cut-off is when all patients from arm 2-4 have completed visit 13a assessments or permanently discontinued treatment.
 
Concizumab (arm 1) data available up until week 56 cut-off will be presented.
	5.6.3

Statistical Analysis Plan W56  
Trial ID: NN7415-4311

UTN: U1111-1225-9670  
EudraCT No.: 2018-004889-34

Date:  
Version:

21 July 2022  
2.0

Status:  
Page:

Final  
26 of 26

